1 INTRODUCTION

1.1 Background

End-stage renal disease (ESRD) is a condition in which there is an irreversible decline in kidney function severe enough to be fatal in the absence of dialysis treatment or kidney transplantation. Reduction in, or absence of, kidney function leads to a host of maladaptive changes including fluid retention (extracellular volume overload), anemia, disturbances of bone and mineral metabolism, dyslipidemia, and protein energy malnutrition (Heye 2012). The incidence of end-stage renal disease in the United States increases by 5% per year, largely due to the growing prevalence of hypertension and diabetes. Currently in the US over 661,000 individuals have been diagnosed with ESRD, and of these, approximately 468,000 are receiving hemodialysis. The average cost of dialysis is \$89,000 per patient, per year, for a total cost to the US medical system of approximately \$42 billion annually, of which \$34 billion is absorbed by Medicare. Approximately 1% of the Medicare population undergoes chronic dialysis, but accounts for 7% of the Medicare budget (USRDS 2015).

Despite improvements over the past 50 years since hemodialysis became available, the mortality rate for patients with ESRD undergoing hemodialysis is 20-25% at one year, with a 5 year survival of only 35% (USRDS 2015). In part, this poor prognosis is due to the compounded impact of concurrent health conditions. Three-quarters of dialysis patients have 5 or more comorbidities, and 90% have cardiovascular disease (USRDS 2005). Hemodialysis access site and venous outflow circuit dysfunction are directly related to morbidity in this population. Inadequate dialysis can lead to cardiopulmonary decompensation, life-threatening electrolyte imbalances, and a multitude of other physiologic complications (Heye 2012). Thus, the ability to effectively complete hemodialysis treatments is critical to improving outcomes.

Vascular access for hemodialysis is achieved via arteriovenous fistula (AVF), arteriovenous graft (AVG) or central venous catheter (CVC). The National Kidney Foundation Kidney Disease Outcomes Quality DCO20-036_09OCT2020

Confidential

Page 3 of 34

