7 ADVERSE EVENTS

7.1 Definitions

Adverse Event (AE)

An adverse event (AE) is any untoward medical occurrence in a subject (regardless of treatment group) that may or may not have a causal relationship with the study procedure. An AE therefore can be any unfavorable or unintended sign (including a clinically significant abnormal laboratory finding, for example), symptom, or disease temporally associated with the use of a medicinal product or procedure, whether or not considered related to the product or procedure. A serious adverse event (SAE) is any untoward medical occurrence that meets any of the criteria for an SAE as defined below.

Subjects should be instructed to report any AE that they experience to the Investigator or Study Coordinator. Adverse events (AE) will be collected starting on the date of study procedure. AEs will be re-assessed at 30 days, 3 months, 6 months, and 12 months, and at any additional interim visit. AEs occurring during the study procedure and the protocol-defined 12 month follow-up period should be recorded on the appropriate AE CRF. It is important that the Investigators record AE terms accurately and consistently throughout the study. Wherever possible, a specific disease or syndrome should be reported

on the CRF rather than the associated individual signs and symptoms (e.g., diabetes mellitus instead of hyperglycemia). If observed or reported signs or symptoms are not considered a component of a specific disease or syndrome by the Investigator, they should be recorded as separate AEs on the CRF. For this study venous outflow obstructions will not be considered adverse events because they will be captured in the calculation of Assisted Primary Patency of the target lesion, Assisted Primary Patency of the venous outflow circuit, and Index of Patency Function.

Serious Adverse Event (SAE)

A serious adverse event (SAE) is any adverse event, regardless of causality that:

- Results in death
- Is life-threatening, where life-threatening means that the subject was at immediate risk of death from the reaction as it occurred, i.e., it does not include a reaction which hypothetically might have caused death had it occurred in a more severe form.

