Under this protocol, scheduled hospitalizations or elective surgical procedures will not be considered SAEs. Deaths due to renal disease progression will not be considered SAEs.

Unanticipated Adverse Device Effect (UADE)

An unanticipated adverse device effect (UADE) is any serious adverse effect on health or safety, any life-threatening problem or death caused by, or associated with a device, if that effect, problem, or death was not previously identified in nature, severity, or degree of incidence in the application; or any other unanticipated serious problem associated with a device that relates to the rights, safety, or welfare of subjects.

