Serious Adverse Events (SAE) that occur following the signature of the informed consent but prior to treatment will not be reported. Deaths due to disease progression will not be considered SAEs, but must be reported to the sponsor within 24 hours of site notification of the event using the electronic Death Report form.

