8 DATA MONITORING/CLINICAL EVENTS COMMITTEE & SAFETY STOPPING RULES

A Data Monitoring/Clinical Events Committee (DMC/CEC) will be formed consisting of at least 3 individuals with expertise and experience in clinical trials, and safety evaluations, but without direct involvement in the conduct of the study. The exact responsibilities, procedures, and guidelines used to manage the DMC/CEC are described in a separate charter.

Any SAE or UADE resulting in surgery or death will trigger a DMC/CEC meeting. The study will stop at 1 SAE or UADE unless the DMC/CEC determines that the event was not primarily due to the study device or procedure. The DMC/CEC will review and adjudicate all target lesion and access circuit interventions performed after the study procedure.

In addition, termination or modification may be recommended for any other perceived safety concern based on clinical judgment of the DMC members.

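### Deaths classed as disease progression are exempt from SAE status, so as written they need not reach the DMC/CEC

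*Combined protocol and SAP*

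**What the plan says.** Four parts of the combined protocol and SAP bear on this.

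- **Section 7.1, general definition.** "A serious adverse event (SAE) is any adverse event, regardless of causality that" meets one of a list of criteria, the first of which is death.
- **Section 7.1, exception.** "Deaths due to renal disease progression will not be considered SAEs".
- **Section 7.2, exception repeated.** "Deaths due to disease progression will not be considered SAEs", here without the word renal, "but must be reported to the sponsor within 24 hours of site notification of the event using the electronic Death Report form". No onward step to the committee is stated.
- **Section 8, committee trigger and stopping rule.** "Any SAE or UADE resulting in surgery or death will trigger a DMC/CEC meeting". In addition, one SAE or UADE halts the trial unless the committee finds that neither the device nor the procedure was its main cause. The committee's stated adjudication task is to review later interventions on the target lesion and access circuit; deaths are not named. Its detailed responsibilities are left to a separate charter.

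Death is also one of the three outcomes in the 30-day primary safety endpoint (Sections 2.1, 4 and 9). There it counts only when it results from a safety event affecting the access or venous outflow circuit.

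**The concern.** In a first-in-human device study, the committee outside the conduct of the trial is the main check on whether a death was related to the device. Here a cause-of-death label that the protocol does not define decides whether a death is an SAE, and SAE status decides whether Section 8 applies. The label takes effect before the committee has seen the case.

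The label is also hard to apply cleanly in this population. Section 1.1 states: "Inadequate dialysis can lead to cardiopulmonary decompensation, life-threatening electrolyte imbalances" and other complications. Inadequate dialysis is what a failing outflow circuit can produce, so a death linked to circuit failure may resemble a death from the underlying renal disease. Section 7.1 adds that venous outflow obstructions are not recorded as adverse events, because the patency measures capture them. The obstruction that might connect the device to the death is then not an AE, and the death itself may not be an SAE.

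**Working it through.** The plan gives no figure on this point, so there is nothing to reproduce. The main check sets the provisions side by side.

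**Route of a fatal event under the current text**

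| Step | Death not exempted | Death classed as progression |
|---|---|---|
| SAE status | SAE (7.1) | Not an SAE (7.1, 7.2) |
| Report to sponsor | 24 hours, SAE form (7.3) | 24 hours, Death Report form (7.2) |
| DMC/CEC meeting | Triggered (8) | Not triggered unless a UADE |
| Stopping rule | Applies (8) | Does not apply unless a UADE |
| Named in adjudication scope | No; interventions only (8) | No; interventions only (8) |

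The sponsor learns of both kinds of death within 24 hours. What the exception removes is the consequence in Section 8. Adjudicating interventions does not close the gap, because a circuit failure that ends in death without a further intervention leaves no intervention to adjudicate.

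**Wording.** Section 7.1 exempts progression of renal disease; Section 7.2 exempts disease progression without qualification. Neither term is defined, and neither section says who makes the classification.

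**Scale, all-cause deaths only**

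Inputs: N = 50 (Sections 4 and 9, approximate); one-year mortality m = 20-25% on hemodialysis (Section 1.1). A constant hazard over the year is assumed.

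- Deaths by 12 months = 50 × m: 50 × 0.20 = 10; 50 × 0.25 = 12.5.
- 30-day risk = 1 − (1 − m)^(30/365): 0.0182 for m = 0.20; 0.0234 for m = 0.25.
- Deaths by day 30 = 50 × 30-day risk: 0.91 and 1.17.
- Chance of at least one death by day 30 = 1 − (1 − 30-day risk)^50: 0.60 and 0.69.

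These are upper-end figures, since Section 3.2 excludes subjects with a life expectancy of 12 months or less. With an assumed one-year mortality of 5-10%, the results are 2.5 to 5 deaths by 12 months, 0.21 to 0.43 by day 30, and a chance of 0.19 to 0.35 of at least one by day 30.

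The share of deaths that would be classed as progression, and the share of those linked to the circuit, are not in the documents. The number of deaths bypassing the committee cannot be computed.

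**The case against.** Several points on the other side are sound.

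- **The deaths are not hidden.** The sponsor receives each one within 24 hours, and nothing forbids passing it on.
- **Other routes exist.** A death associated with the device, and not previously identified in nature, severity or degree of incidence, is a UADE and triggers the committee. A life-threatening event or unplanned hospitalization before death remains an SAE, reportable whether or not related. The committee may also act on any other safety concern.
- **The charter may cover deaths.** It is a separate document that I have not seen.
- **The wording difference may be harmless.** In an end-stage renal disease study, both sentences can be read as meaning the same disease.

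These narrow the gap but do not close it. The UADE route requires someone first to connect the death with the device. An outflow obstruction before death is not an AE, so it gives no SAE of its own. The committee can act on a concern only if it hears of the death. If the charter covers deaths, a cross-reference is still needed so that the protocol agrees with it.

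Three stronger readings are tempting and are not supported:

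- **That the exception biases the primary safety endpoint.** The endpoint is not defined through SAE status, so these deaths are not dropped from it. One subject in 50 is 2 percentage points, but nothing in the text shows that such a shift would occur.
- **That the implanting site assigns the cause.** Section 7.2 gives the investigator the judgement of device or procedure relatedness. Who classes a death as progression is not stated.
- **That 10-12.5 deaths would escape review.** That figure is all-cause. The exception reaches only a subset of unknown size, and deaths after day 30 cannot affect a 30-day endpoint.

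**Conclusion.** The point holds as a gap in independent review. Followed as written, Sections 7.1, 7.2 and 8 allow a death classed as disease progression to bypass both the DMC/CEC meeting trigger and the stopping rule, unless it is a UADE or the unseen charter covers it. Section 1.1 and the treatment of obstructions in Section 7.1 make it plausible that a circuit-related death could be classed this way; the documents do not say that it would be.

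An effect on the primary safety endpoint is possible only, and cannot be sized. The mortality figures show that some deaths are likely during follow-up, so the rule will probably be used. They rest on the protocol's background rate, a constant hazard and N = 50, and do not count misclassified deaths. The change is worth making because a stated rule creates the gap and closing it is cheap.

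**What to change.** 1. Use one defined term for the exempted deaths in Sections 7.1 and 7.2, and say who applies it.
2. Limit the exception to expedited SAE reporting, keeping the existing 24-hour Death Report.
3. State in Section 8 that every Death Report through 12 months goes to the DMC/CEC, whatever cause is given, and that the committee adjudicates the cause and whether the death meets the primary safety endpoint.
4. Reconcile the general SAE definition, both exception sentences, Section 8 and the charter. In particular, say how these deaths relate to the stopping rule: once the exception covers reporting only, they would fall within that rule's words. How the rule should treat them is for the sponsor and committee to settle.

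**Cost.** A few sentences in Sections 7.1, 7.2 and 8 and a check of the charter. No new data are needed, since the Death Report already exists. The added work is a few more reports for the existing committee: about 2.5 to 12.5 all-cause deaths over 12 months across the mortality range above, some of which would reach it anyway.

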7.2 Adverse Event Reporting

The Investigators are responsible for monitoring the safety of subjects who have been enrolled in this study. All adverse events (AE) considered to be related to study procedure will be followed until the event resolves or has reached a final outcome. AEs will be evaluated for severity according to the following Common Terminology Criteria for Adverse Events (CTCAE) grading scale:

- Grade 1: Mild; asymptomatic or mild symptoms; clinical or diagnostic observations only; intervention not indicated.
- Grade 2: Moderate; minimal, local or noninvasive intervention indicated; limiting age appropriate instrumental ADL.
- Grade 3: Severe or medically significant but not immediately life-threatening; hospitalization or prolongation of hospitalization indicated; disabling; limiting self care ADL.
- Grade 4: Life-threatening consequences; urgent intervention indicated.
- Grade 5: Death related to AE.

The Investigator, based on his/her clinical judgment and the following definitions, must determine the relationship of the adverse event to the device and/or procedure:

- None: The AE/SAE does not follow reasonable temporal sequence from the time of study procedure and/or does not follow a known response pattern to the study procedure and is likely to have been produced by other factors.
- Possible: The AE/SAE follows a reasonable temporal sequence from the time of study procedure, and/or follows a known response pattern to the study procedure, but could have been produced by other factors.
- Probable: The AE/SAE follows a reasonable temporal sequence from the time of study procedure, follows a known response pattern to the study procedure, and cannot reasonably have been produced by other factors.
- Definite: The AE/SAE follows a reasonable temporal sequence from the time of study procedure; follows a known response pattern to the study procedure; and cannot have been produced by other factors.

Investigators are required to document all device and/or study procedure related AEs occurring during the study commencing with the date of study procedure through the protocol defined 12 month post-treatment follow-up period, or discontinuation, death, or loss to follow-up subject. AEs that occur following the signature of informed consent but prior to treatment will not be captured.

Serious Adverse Events (SAE) that occur following the signature of the informed consent but prior to treatment will not be reported. Deaths due to disease progression will not be considered SAEs, but must be reported to the sponsor within 24 hours of site notification of the event using the electronic Death Report form.

7.3 Serious Adverse Event Reporting

Any unanticipated adverse event or SAE that occurs during study procedure through the 12 month follow-up period, whether or not related to the study procedures, must be reported to the Sponsor within 24 hours of site knowledge of the event on the electronic SAE form. The SAE must be completely described on the AE CRF as well as the electronic SAE report form.

Safety Contact Information:
[REDACTED]
[REDACTED]
[REDACTED]

8 DATA MONITORING/CLINICAL EVENTS COMMITTEE & SAFETY STOPPING RULES

A Data Monitoring/Clinical Events Committee (DMC/CEC) will be formed consisting of at least 3 individuals with expertise and experience in clinical trials, and safety evaluations, but without direct involvement in the conduct of the study. The exact responsibilities, procedures, and guidelines used to manage the DMC/CEC are described in a separate charter.

Any SAE or UADE resulting in surgery or death will trigger a DMC/CEC meeting. The study will stop at 1 SAE or UADE unless the DMC/CEC determines that the event was not primarily due to the study device or procedure. The DMC/CEC will review and adjudicate all target lesion and access circuit interventions performed after the study procedure.

In addition, termination or modification may be recommended for any other perceived safety concern based on clinical judgment of the DMC members.

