2.2 Secondary Objectives

- Proportion of subjects with Target Lesion Primary Patency at 3, 6 and 12 months
- Proportion of subjects with Assisted Primary Patency of the target lesion at 30 days, 3, 6 and 12 months
 - Time to loss of Assisted Primary Patency of the target lesion is defined as time following study procedure until uncorrectable target lesion occlusion
- Proportion of subjects with Primary Patency of the venous outflow circuit at 30 days, 3, 6, and 12months
 - Time to loss of Primary Patency of the venous outflow circuit is defined as the time following initial study procedure until the next venous outflow circuit intervention
- Proportion of subjects with Assisted Primary Patency of the venous outflow circuit at 30 days, 3, 6 and 12 months.

- Time to loss of Assisted Primary Patency of the venous outflow circuit is defined as the time following initial study procedure until complete access abandonment.
- Index of Patency Function at 3, 6 and 12 months, defined as time from initial study procedure to complete access abandonment divided by number of venous outflow circuit re-interventions to maintain hemodialysis
- Procedure or device related adverse events at 3, 6 and 12 months
- Clinical Success
 - The resumption of successful dialysis through existing access for at least one session following initial study procedure
- Anatomic Success
 - Less than 30% residual stenosis immediately following study procedure
- Procedural Success
 - The achievement of both clinical and anatomic success

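### Anticipated graft occlusions leading to surgery or hospitalization have no stated 24-hour report; those leading to surgery miss the SAE meeting trigger, and access loss without intervention is not sent to the DMC/CEC

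*Combined protocol and SAP*

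**What the plan says.** Four parts of the protocol bear on this.

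- **What counts as an event.** Section 7.1 states: "For this study venous outflow obstructions will not be considered adverse events because they will be captured in the calculation of Assisted Primary Patency". The sentence goes on to name the target lesion, the venous outflow circuit and the Index of Patency Function. The same section defines seriousness within adverse events: "A serious adverse event (SAE) is any adverse event, regardless of causality that", followed by the usual criteria.
- **What is reported fast.** Section 7.3 requires SAEs and unanticipated adverse events to reach the sponsor within 24 hours of the site learning of them. Section 7.2 adds a 24-hour Death Report for deaths from disease progression, which are not SAEs.
- **What reaches the committee.** Section 8: "Any SAE or UADE resulting in surgery or death will trigger a DMC/CEC meeting". The study stops at one SAE or UADE unless the DMC/CEC finds that the device or procedure was not the main cause. The committee also adjudicates interventions on the target lesion and access circuit, and its members may raise any other safety concern. Details are left to a charter.
- **What the endpoints count.** Section 2.2: "Time to loss of Assisted Primary Patency of the target lesion is defined as time following study procedure until uncorrectable target lesion occlusion". For the circuit: "Time to loss of Assisted Primary Patency of the venous outflow circuit is defined as the time following initial study procedure until complete access abandonment".

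**The concern.** The reason given for the exclusion is that the patency endpoints already capture obstructions. Capture for analysis is not the same as prompt notice to a safety committee. The only interim analysis in Section 9 waits until every subject has completed the 6-month visit or left the study before it. The primary safety endpoint carries the same exclusion (Sections 2.1, 4 and 9), so it does not bring these events forward either.

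This is a first-in-human implant. Section 3.2 excludes a thrombosed access and one expected to be abandoned within 3 months, so early occlusion or loss of the access is a new event after implantation. At stake is whether such an event, when it has serious consequences, reaches the sponsor and the committee promptly.

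**Working it through.** No arithmetic applies, and the plan states no figure on this point. The check is to follow an occlusion through the definitions.

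1. Section 7.1: a venous outflow obstruction is not an adverse event. The exclusion names Assisted Primary Patency of the target lesion as the measure that captures it, and the event for that measure is uncorrectable target lesion occlusion (Section 2.2). Occlusion of the target lesion, or of the graft in it, is therefore within the exclusion.
2. Section 7.1: an SAE must be an adverse event, so the occlusion cannot be an SAE whatever follows from it.
3. Section 7.3 covers SAEs and unanticipated adverse events, so it does not reach the occlusion.
4. The SAE limb of the Section 8 trigger does not reach it. The UADE limb does so only if the effect was "not previously identified in nature, severity, or degree of incidence in the application", or under the general limb: "or any other unanticipated serious problem associated with a device that relates to the rights, safety, or welfare of subjects". An anticipated occlusion meets neither.

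The result by consequence, for an anticipated occlusion:

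| Consequence | 24-hour report | Meeting trigger | Adjudication |
|---|---|---|---|
| Surgery on the target lesion or access circuit | None stated | Outside the SAE limb | Yes, no timing stated |
| Hospitalization | None stated | Not applicable: the trigger names only surgery and death, even for SAEs | Only if an intervention was done |
| Death classed as disease progression | Yes, Death Report | Not through that form | Only if an intervention was done |
| Death with a separate fatal adverse event | Yes, as an SAE | Yes | Only if an intervention was done |
| Death attributed solely to the obstruction, not to disease progression | None stated, read literally | Outside the SAE limb | Only if an intervention was done |
| Uncorrectable occlusion or abandonment, no intervention | None stated | Outside the SAE limb | Not listed |

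For the last row, the other routes were checked as well. The Section 5 visits and Appendix A record interventions. Section 12 has sites ask dialysis centers about revisions and lets them obtain subject status there. Section 6 withdraws a subject whose access is abandoned and records the reason on the end of study form. The outcome is thus recorded, and it counts as loss of Assisted Primary Patency of the circuit. None of these texts sends it to the DMC/CEC, whereas any repeat angioplasty of the target lesion is adjudicated.

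**The case against.** The exclusion is deliberate and consistent across the protocol, and obstruction is the expected failure mode in this population. Making each one an SAE would expose the study to its one-event stop for expected outcomes. That stands, and the point leaves the exclusion and the stop alone.

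Other safeguards exist. Interventions are adjudicated, members may raise any concern, unexpected occlusions can be UADEs, and a distinct complication such as infection or bleeding remains an SAE. The charter may set timing and referral. All of this stands, and it limits the gap without closing it: the discretionary clause works only on what reaches the committee, and the charter cannot be checked.

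Whether an occlusion is anticipated depends on the application, which is not available. If surgical or fatal occlusion was not identified there, it is a UADE and the Section 8 trigger and stop already apply. The size of the gap is therefore unknown.

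Three stronger readings are tempting and not supported:

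- *Fatal occlusions go unreported.* Two 24-hour routes exist for deaths. Only a death put down solely to the obstruction, and not to disease progression, lacks one.
- *Reporting is delayed by the months between visits.* Those intervals do not measure an effect of the exclusion, because an SAE treated elsewhere can also reach the site late. The difference starts at site knowledge: 24 hours against no stated limit.
- *Abandonment is lost because required AE documentation ends at "or discontinuation, death, or loss to follow-up subject".* The occlusion and abandonment come before the withdrawal they cause, so this cutoff adds little.

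**Conclusion.** The concern holds in a limited form. It is firm for surgery and hospitalization (no stated 24-hour report), for surgery (outside the SAE limb of the meeting trigger), and for uncorrectable occlusion or abandonment without an intervention (not referred to the committee by the protocol). For death it holds only in that a Death Report does not itself convene a meeting, plus the one narrow case above.

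The number of affected subjects cannot be given, since the documents contain no occlusion rate for this device. No estimate, endpoint definition or primary analysis changes; the gain is in safety oversight and in complete adjudication of patency events.

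Assumptions: that target lesion or graft occlusion counts as venous outflow obstruction, a term the protocol does not define separately; that at least some occlusions are anticipated in the application; and that the charter does not already close the gap. This version widens the 12-month window for COVID-19, so implantation may be complete. The benefit would then be prompt oversight of subjects who carry the device, not decisions about new implants.

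This is a cheap improvement worth making, with medium confidence.

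**What to change.** 1. Section 7.3, add: *A target lesion or stent graft occlusion excluded from adverse events under Section 7.1 that results in surgery, hospitalization, death or abandonment of the access must still be reported to the Sponsor within 24 hours of site knowledge. An event that meets the UADE definition is handled as a UADE.*
2. Section 8, add after the meeting trigger: *Such an event, if it results in surgery or death, convenes a DMC/CEC meeting. Unless it is a UADE or SAE, it does not by itself stop the study.*
3. Section 8, extend adjudication to: *all target lesion and access circuit interventions, and all uncorrectable target lesion occlusions and access abandonments without an intervention.*

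The first edit follows the model of Section 7.2, where disease-progression deaths are not SAEs but are still reported within 24 hours. Tying it to the Section 7.1 exclusion matters: a sentence declaring every graft occlusion or thrombosis not to be an adverse event would widen the exclusion and conflict with the existing stop at one UADE.

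The cost is two sentences in Section 7.3, two in Section 8, one added phrase and a matching charter line, using the existing committee and electronic forms. The downside is a few extra reports, meetings and adjudications; the documents do not allow a count. Restenosis without occlusion is outside the new text. Catheter-based re-intervention, which Section 1.1 distinguishes from surgery, would not convene a meeting.
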